### **8.3 Time Period and Frequency for Event Assessment and Follow-Up**

The occurrence of an AE or SAE may come to the attention of study personnel during study visits. All AEs including local and systemic reactions not meeting the criteria for SAEs will be captured on the appropriate visit note. Information to be collected includes event description, time of onset, clinician's assessment of severity, relationship to study product (assessed only by those with the training and authority to make a diagnosis), and time of resolution/stabilization of the event. All AEs occurring while on study must be documented appropriately regardless of relationship. All AEs will be followed to adequate resolution.

Any medical condition that is present at the time that the participant is screened will be considered as baseline and not reported as an AE. However, if the study participant's condition deteriorates at any time during the study, it will be recorded as an AE. UPs will be recorded in the data collection system throughout the study.

Changes in the severity of an AE will be documented to allow an assessment of the duration of the event at each level of severity to be performed. AEs characterized as intermittent require documentation of onset and duration of each episode.

The PI will record all reportable events with start dates occurring any time after informed consent is obtained until 7 (for non-serious AEs) or 30 days (for SAEs) after the last day of study participation. At each study visit, the investigator will inquire about the occurrence of AE/SAEs since the last visit. Events will be followed for outcome information until resolution or stabilization.

All unresolved adverse events should be followed by the investigator until the events are resolved, the subject is lost to follow-up, or the adverse event is otherwise explained. At the last scheduled visit, the investigator should instruct each subject to report any subsequent event(s) that the subject, or the subject's personal physician, believes might reasonably be related to participation in this study.

[figure not shown]
### **8.4 Reporting Procedures – Notifying the IRB**

#### **8.4.1 Adverse Event Reporting**

AEs will be documented in the visit note including an event description, time of onset, clinician's assessment of severity, relationship to study product (assessed only by those with the training and authority to make a diagnosis), and time of resolution/stabilization of the event. AEs occurring within 7 days from end of participant study duration. The study staff that are responsible for completing AE reports are study administrators that first hear the participant report the event. The study staff that are responsible for signing off on AE reports include the principal investigator and/or study administrators recorded in key roles in the investigational protocol. All study administrators in key roles and the principal investigator will receive notification of all AEs. AEs are reportable to the IRB within 5 calendar days if the event or new information is consistent with the following:

- new information indicating a change to the risks or potential benefits of the research, in terms of severity or frequency (such as analysis indicating more severe or frequent side effect or an FDA labeling change or withdrawal from market)
- protocol deviation or violation, only if one or more of the following criteria is met:
  1. it was intended to eliminate apparent immediate hazard to a research participant
  2. it was harmful (caused harm to participants or others or placed them at increased risk of harm)
  3. it represented possibly serious or continued noncompliance
- a complaint unresolved by the research team or that indicates increased or unexpected risks
- incarceration of a participant, when the principal investigator believes it is in the best interest of the participant to remain in the study
- an unanticipated adverse device effect
- new information about the effect on health or safety or any life-threatening problem or death caused by or associated with a device, if that effect, problem, or death was not previously identified in nature, severity, or degree of incidence

[figure not shown]

#### 8.4.2 Serious Adverse Event Reporting

SAEs will be documented in the visit note including an event description, time of onset, clinician's assessment of severity, relationship to study product (assessed only by those with the training and authority to make a diagnosis), and time of resolution/stabilization of the event. SAEs occurring with 30 days from end of participant study duration. The study staff that are responsible for completing SAE reports are study administrators that first hear the participant report the event. The study staff that are responsible for signing off on SAE reports include the principal investigator and/or study administrators recorded in key roles in the investigational protocol. All study administrators in key roles and the principal investigator will receive notification of all SAEs. SAEs are reportable to the IRB within 5 calendar days if the event or new information is consistent with the following:

- new information indicating a change to the risks or potential benefits of the research, in terms of severity or frequency (such as analysis indicating more severe or frequent side effect or an FDA labeling change or withdrawal from market)
- protocol deviation or violation, only if one or more of the following criteria is met:
  1. it was intended to eliminate apparent immediate hazard to a research participant
  2. it was harmful (caused harm to participants or others or placed them at increased risk of harm)
  3. it represented possibly serious or continued noncompliance
- a complaint unresolved by the research team or that indicates increased or unexpected risks
- incarceration of a participant, when the principal investigator believes it is in the best interest of the participant to remain in the study
- an unanticipated adverse device effect
- new information about the effect on health or safety or any life-threatening problem or death caused by or associated with a device, if that effect, problem, or death was not previously identified in nature, severity, or degree of incidence

[figure not shown]
### 8.4.3 Unanticipated Problem Reporting

Incidents or events that meet the criteria for UPs indicated in section 8.1.3 require the creation and completion of an UP report form. It is the site investigator's responsibility to report UPs to their IRB. The UP report will include the following information:

- Protocol identifying information: protocol title and number, PI's name, and the IRB project number;
- A detailed description of the event, incident, experience, or outcome;
- An explanation of the basis for determining that the event, incident, experience, or outcome represents an UP;
- A description of any changes to the protocol or other corrective actions that have been taken or are proposed in response to the UP.

To satisfy the requirement for prompt reporting, UPs will be reported using the following timeline:

- UPs will be reported to the IRB within 5 calendar days of the investigator becoming aware of the event.

### 8.5 Study Halting Rules

The study will be halted when three grade 3 AEs determined to be “related” are reported to the IRB.

## 9 Clinical Monitoring

Clinical site monitoring will be conducted to ensure that the rights and well-being of human subjects are protected, that the reported trial data are accurate, complete, and verifiable, and that the conduct of the trial is in compliance with the currently approved protocol/amendment(s), with GCP, and with applicable regulatory requirement(s).

- Site Investigators, , [name], [name], [name] and [name] will conduct the monitoring activities and report to the medical monitor [name]. These doctors are PGY-3 and PGY-4 dermatology residents, and are not members of the telemedicine team.
- [name] (study PI) is a member of the telemedicine team and needs to remain blinded to the data until the study conclusion, so he cannot conduct the clinical monitoring. The monitoring team will report their monthly findings to [name] while maintaining blinding of specific participant identifiable details.
- The monitoring will consist of monthly reviews of all the CRFs and the image database to ensure that all records are complete (i.e. no missing data). They will review the frequency and nature of any adverse events and participant withdrawals from the study. They will also review the screening and enrollment data to insure that eligible participants are not being incorrectly excluded from the study, and that ineligible participants are being appropriately excluded.

## 10 Statistical Considerations

### 10.1 Statistical Hypotheses

Primary endpoint:

We will not perform hypothesis testing in this pilot study; we will use descriptive statistics and summarize preliminary evidence from this pilot study.

Secondary endpoints

We will not perform hypothesis testing in this pilot study.

### 10.2 Analysis Datasets

All eligible lesions evaluated by both the teledermatologists and the in-person dermatologist.

### 10.3 Description of Statistical Methods

#### 10.3.1 General Approach

The general approach will be to determine the agreement between in-person recommendation and the telemedicine (tele) recommendation. For this reason the data will be categorical in nature and the specific measures to be assessed are described below. We will also examine the performance characteristics of the tele approach (e.g. sensitivity, specificity, etc.) using the in-person dermatologist biopsy decision as the 'gold standard'(primary endpoint). However, it is possible that with respect to the pathology results (secondary endpoint), the tele approach may have a higher sensitivity and specificity to diagnose skin cancer than the in-person dermatologist. For this reason, we will also examine the performance of the tele and in-person biopsy decisions against the pathology results as the 'gold standard'.

#### 10.3.2 Analysis of the Primary Efficacy Endpoint(s)

To determine the agreement between in-person recommendation and the telemedicine (tele) recommendation we can calculate the number of discordant benign vs. malignant diagnoses; specifically, the number of subjects that were recommended a biopsy from the in-person dermatologist but were recommended no biopsy from the teledermatology team, and the number of subjects that were recommended no biopsy from the in-person dermatologist but biopsy by the teledermatologist team. We can calculate the Kappa coefficient as a measure of the degree of concordance or agreement with confidence intervals. We can also calculate "sensitivity" and "specificity" of the tele method assuming in-person diagnosis as the gold standard. Similarly, we can separately evaluate the agreement between in-person and: 1) dermoscopy alone; and 2) Nevisense (EIS score  $\geq 4$ ) without dermoscopy. We will also estimate the improvement (if any) of using both methods compared to one method. We expect the Kappa coefficient to be close to one, and high "sensitivity" and "specificity" (close to 1) for the SpotCheck method assuming in-person diagnosis as the gold standard.

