Duration of IP administration	Clinical and dermoscopic image acquisition for teledermatologist evaluation will take <2 minutes per lesions, and Nevisense data acquisition will take <2 minutes per lesion
Population	At least 18 years of age Females and Males
Study Sites	NYU School of Medicine The Ronald O. Perelman Department of Dermatology Ambulatory Care Center Dermatology Clinical Trials Unit [name]
Number of participants	650 enrolled participants
Description of Study Agent/Procedure	Telemedicine evaluation using combined dermoscopic imaging with DermLite Cam (3Gen) and/or Barco Demetra and electrical impedance spectroscopy using Nevisense 3.0
Reference Therapy	In-person dermatologist evaluation

CONFIDENTIAL

[figure not shown]
Key Procedures	Clinical and dermoscopic imaging of skin lesions, Nevisense measurement of skin lesion electrical impedance. Possible skin biopsy for lesion(s) identified as concerning for malignancy
Statistical Analysis	Percent agreement of biopsy recommendation in diagnostic intervention compared to control. For biopsied lesions, sensitivity and specificity of in-person dermatologist and teledermatologist evaluation for skin cancer diagnosis will also be determined. Success by patient centered outcomes will be analyzed by questionnaires using Likert scales.

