**Schematic of Study Design**

1. Lesions must not be in a hair-bearing area on the scalp, in the mouth, on the lips, genitalia, nails, around/on the eyes, inside ear.
2. All lesions of all subjects will be evaluated by teledermatologist team. If at least one of three possible lesions was not recommended for biopsy by the in-person dermatologist, this subject will receive a telemedicine consensus recommendation report to (or not to) biopsy within 3 business days of participant evaluation. If all eligible lesions were recommended for biopsy by the in-person dermatologist, this subject will not receive the telemedicine evaluation report.
3. The following lesions will have clinical and dermoscopic image taken, but will not have a Nevisense score: Lesions on an acral site, lesions with recurrence after biopsy/excision, lesions in a scar, lesions with foreign material (e.g. tattoo, splinter, etc), lesions in an area of active sunburn, lesions on a stalk, lesions with crust. Bleeding or ulcerated lesions are will only have a clinical image taken (no dermoscopic or Nevisense score).
4. Current gold standard evaluation for skin lesion of concern. For subjects with more than 1 lesion evaluated, they may have 1 or more recommended for biopsy by the in-person dermatologist (or equally 1 or more recommended for no biopsy by the in-person dermatologist).

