## **3 Objectives and Purpose**

### **3.1 Primary Objective**

The primary objective of the study is to assess the concordance in biopsy recommendations between the in-person dermatologist evaluation and the enhanced telemedicine evaluation of participant-identified skin lesions concerning for skin cancer in a walk-in clinic setting.

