In addition to the DermLite Cam images, a study specific camera or EPIC HAIKU will be used to acquire 3 clinical images of <5 seconds per lesion (from 6 inches away, 12 inches away, and 18 inches away). Images will be stored in the patient's medical record in Epic, to which the teledermatology team has access. Clinical images taken through Epic Haiku or the study specific camera will not be stored elsewhere. Images taken with the study specific camera will be deleted from the camera once images are uploaded to EPIC.

The Barco Demetra device will be used to acquire 3 images of <5 seconds per lesion (one clinical, one polarized dermoscopic, and one non-polarized dermoscopic) as well as 3 additional clinical images of <5 seconds per lesion (from 6 inches away, 12 inches away, and 18 inches away). Images will be stored in the authenticated and data-encrypted Demetra Cloud accessible via the web by the telemedicine team in the NYU Department of Dermatology Pigmented Lesion Clinic. The telemedicine dermatology team will review the images using this dedicated cloud software. Clinical and dermoscopic images taken by the Barco Demetra device will not be stored elsewhere.

Lesions with bleeding or ulceration will only have a clinical image taken and not have a dermoscopic image taken.

The telemedicine dermatology team will consist of [name], [name], and [name], who are all pigmented lesion experts. They will be listed as co-investigators. They will submit independent, blinded to each other, diagnoses for each lesion on REDCap. If at least one teledermatologist believes the lesion to be a malignant diagnosis, the lesion will be recommended for biopsy. If the participant has not already had the lesion biopsied by the in-person recommendation, the participant will be told this concern for malignancy and telemedicine recommendation for biopsy.

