### **7.3 Study Schedule**

As described below, the study schedule includes a variable number of visits that depend upon the outcome of the initial evaluation. Briefly, 3 outcomes are possible:

- 1) The lesion(s) is diagnosed as not suspicious for skin cancer by both the in-person dermatologist and telemedicine team, and no biopsy is recommended
- 2) The lesion(s) is diagnosed as not suspicious for skin cancer by the in-person dermatologist, but suspicious for skin cancer by the telemedicine team, and a biopsy is recommended when the telemedicine team results are communicated to the participant
- 3) The lesion(s) is diagnosed suspicious for skin cancer by the in-person dermatologist, and a biopsy is performed at the initial visit, or scheduled to be performed at a follow up visit. In this scenario, the recommendation of the telemedicine team will not be communicated to the participant since we do not yet know if a 'no biopsy' recommendation by the telemedicine team is a safe alternative to a 'biopsy' recommendation by the in-person dermatologist.

Based on the outcomes described above, the participant will have either 1 visit and 1 phone call (initial evaluation and follow-up phone call), or an additional visit for telemedicine recommended biopsy and an additional phone call with biopsy results.

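### Section 10.3.2 words both primary discordance counts as numbers of subjects although the plan is otherwise at lesion level, and its confidence intervals do not allow for several lesions per person.

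*Combined protocol and SAP*

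**What the plan says.** - Section 10.3.2 gives one discordant cell of the primary agreement table as "the number of subjects that were recommended a biopsy from the in-person dermatologist but were recommended no biopsy from the teledermatology team". The opposite cell, where only telemedicine asks for a biopsy, has the same unit: "the number of subjects that were recommended no biopsy from the in-person dermatologist but biopsy by the teledermatologist team". The section adds kappa with confidence intervals, and sensitivity and specificity against the in-person decision. It names no unit for these.
- Section 10.2 defines the dataset as "All eligible lesions evaluated by both the teledermatologists and the in-person dermatologist".
- The primary objective (3.1) compares the in-person evaluation with "the enhanced telemedicine evaluation of participant-identified skin lesions concerning for skin cancer in a walk-in clinic setting".
- Section 6.1.4 sets the telemedicine call lesion by lesion: "If at least one teledermatologist believes the lesion to be a malignant diagnosis, the lesion will be recommended for biopsy".
- Footnote 4 of the design schematic says of subjects with more than one lesion that "they may have 1 or more recommended for biopsy by the in-person dermatologist (or equally 1 or more recommended for no biopsy" by that dermatologist.
- The Protocol Summary lists "Percent agreement of biopsy recommendation in diagnostic intervention compared to control" without a unit in that line, although Aim 1 in the same table is about evaluations of lesions.
- Section 10.4 expects up to 500 participants with 1 to 3 lesions each, averaging 2, hence about 1000 lesions, and a 10% biopsy recommendation rate.
- Section 10.1 rules out hypothesis testing.

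**The concern.** A person with one lesion recommended for biopsy and one not recommended has no single biopsy status. If subjects are counted, someone must decide how such a person enters the two-by-two table, and the plan does not say.

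The nearest candidates do not fill the gap. The any-reader rule in 6.1.4 and 10.5 combines readers, not lesions. Schematic footnote 2 and the telephone call in 7.3.3 decide who is told the telemedicine result. The Visit 2 heading directs a visit. The biopsy strata in 10.3.3 apply to questionnaires.

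The cell for in-person biopsy and telemedicine no-biopsy matters most, because 7.3 leaves open whether a no-biopsy "recommendation by the telemedicine team is a safe alternative". Under one plausible rule, a person in whom telemedicine flags one lesion but passes over another that the in-person dermatologist would biopsy counts as concordant, and the missed lesion leaves that cell.

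The second issue arises once lesions are the unit. Lesions from one person may be judged alike, and an interval that treats them as independent can then be too narrow. Section 10.3.2 does not say how its intervals are computed.

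**Working it through.** **The plan's own figures (10.4).** 500 × 2 = 1000 lesions. 10% of 500 to 1000 is 50 to 100 biopsies recommended, and 90% is 450 to 900 not recommended. All reproduce. The upper ends are lesion counts at 2 per person; the lower ends correspond to one lesion per person.

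**Assumptions not in the documents.** 500 participants; 1, 2 or 3 lesions equally likely (mean 2); 10% of lesions positive in person; telemedicine sensitivity 0.90 and specificity 0.97 against the in-person call.

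**Lesion level.**
- In-person-only lesions: 1000 × 0.10 × 0.10 = 10.
- Telemedicine-only lesions: 1000 × 0.90 × 0.03 = 27.
- Agreement: 0.10 × 0.90 + 0.90 × 0.97 = 0.963.
- Telemedicine positive: 0.090 + 0.027 = 0.117. Chance agreement: 0.10 × 0.117 + 0.90 × 0.883 = 0.8064. Kappa: (0.963 − 0.8064)/(1 − 0.8064) = 0.81.

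**In-person-only subjects, all calls independent within person.** Average over n = 1, 2, 3 lesions and multiply by 500.
- At least one lesion discordant in that direction: 1 − 0.99ⁿ = 0.0100, 0.0199, 0.0297. Mean 0.0199, giving 9.9 subjects.
- Any-lesion-positive rule (a subject is biopsy for an evaluator if that evaluator flags at least one lesion): 0.883ⁿ − 0.873ⁿ = 0.0100, 0.0176, 0.0231. Mean 0.0169, giving 8.4 subjects.
- Opposite cell under the same rule: 0.9ⁿ − 0.873ⁿ = 0.0270, 0.0479, 0.0637. Mean 0.0462. Subject agreement is 1 − 0.0169 − 0.0462 = 0.937, and kappa is 0.80.

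**With within-person correlation (simulation).** In-person positivity has latent correlation 0 / 0.3 / 0.6 (ICC 0 / 0.13 / 0.32). Telemedicine calls, given the in-person call, have latent correlation 0 or 0.6.

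| In-person-only count | Tele calls independent | Tele calls correlated |
|---|---|---|
| Lesions | 10 | 10 |
| Subjects, at least one such lesion | 10.0 / 9.9 / 9.7 | 9.9 / 9.4 / 9.1 |
| Subjects, any-lesion-positive rule | 8.4 / 7.2 / 5.9 | 9.0 / 7.9 / 6.6 |
| In-person-only lesions in people where tele flags another lesion | 15 / 26 / 40% | 8 / 16 / 27% |

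Mixed subjects are common: 80 / 75 / 65% of subjects with any in-person biopsy recommendation also have a no-biopsy lesion. With telemedicine calls independent, any-lesion kappa is 0.80 to 0.79. Over five sensitivity/specificity pairs it differs from lesion kappa by 0.00 to 0.04.

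**Intervals for percent agreement over lesions.**
- Unclustered half-width: 1.96 × √(0.963 × 0.037/1000) = 1.17 points.
- Design effect: 1 + ICC × (E[n²]/E[n] − 1). E[n²] = (1 + 4 + 9)/3 = 14/3 and E[n] = 2, so the multiplier of the ICC is 7/3 − 1 = 4/3.
- Telemedicine calls independent: agreement ICC is about 0, narrowing 0.0 to 0.3%.
- Latent correlation 0.6: agreement ICC 0.15 to 0.19, design effect 1.20 to about 1.26, half-width 1.28 to 1.31 points. Unclustered intervals are 9 to 11% too narrow for agreement and 7 to 11% for kappa.

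**The case against.** The strongest reply is that the unit is largely settled. Aim 1, the primary objective, the dataset, the sample-size text and the lesion-based missing-data exclusions in 10.3.3 all point to lesions. The sentence in 10.3.2 itself opens with discordant diagnoses before turning to subjects. That stands, and it is why loose wording is the likelier explanation. It does not make the sentence right. Section 10.3.3 uses lesions and participants as different units, and the two counts are the only place where the primary discordance is spelled out.

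It is also fair that the reading closest to the words, subjects with at least one lesion discordant in that direction, leaves the in-person-only count almost unchanged at 9 to 10. The telemedicine-only count moves more if calls are correlated, from about 27 lesions to about 23 subjects.

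A reader might infer a much larger distortion, because requiring all of a subject's lesions to be positive would reduce 10 lesions to 2 to 4 subjects. No passage suggests such a rule, so that fall should not be held against the plan.

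On clustering, the documents give no basis for a latent correlation of 0.6, and no planned decision turns on about 0.1 of a percentage point. Both stand, so the narrowing is a possibility and not a finding. For 10.3.3, pathology exists only for biopsied lesions, and in the simulation lesions flagged by either evaluator average only 1.09 to 1.29 per affected person. Little effect is expected there.

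**Conclusion.** The conflict in wording is real, and the counts taken literally lack a rule. The consequence is modest. Under the stated assumptions, about 10 in-person-only lesions would be reported as about 9 to 10 or about 6 to 9 subjects, depending on which of two plausible readings the analyst adopts. The any-lesion-positive reading can hide a missed lesion. Kappa changes little. Intervals for agreement range from about right to 9 to 11% too narrow, depending on a within-person correlation that the documents do not give. The larger count shift arises with independent telemedicine calls and the larger interval effect with correlated ones, so the two should not be added.

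A reader might go further and conclude that the primary analysis has no defined unit or that error rates are compromised. The documents do not support either: 10.2 names lesions, and there is no test whose error rate could be affected. Nor does the 10% biopsy figure, given for subjects in 2.4.1 and readable as per lesion in 10.4, affect the primary analysis. This is a minor point for a descriptive pilot.

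**What to change.** 1. In 10.3.2, replace subjects with lesions in both discordance counts, and state that percent agreement, kappa, sensitivity and specificity are computed over lesions.
2. In 10.3.2, state that 95% intervals account for clustering by participant, either by a bootstrap that resamples participants with all their lesions kept together or by cluster-robust variance. Use the same method in 10.3.3 for consistency.
3. Label any subject-level result as supportive and state its rule, for example that an evaluator's result for a subject is biopsy if that evaluator recommends biopsy of at least one lesion.

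The cost is a few sentences, a few lines of code and possibly slightly wider intervals. No new data are needed.
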